## 7.6 Interim Analyses and Data Monitoring

Data will be reviewed by an independent DMC at regular intervals primarily to evaluate safety during study conduct. The committee will operate independently from the Sponsor and the clinical investigators.

One formal interim analysis of OS is planned, providing the DMC a chance to recommend stopping the trial earlier in case the study treatment shows an overwhelming effect on survival. This interim analysis will be conducted by the independent DMC after approximately half (ie, approximately 335) of the required death events have occurred using the same statistical methods as described in Section 7.3. All data available at the time of clinical data cut for the interim analysis will be included in the interim analysis. Inclusion of additional available data beyond the clinical data cut will be at the discretion of DMC. The nominal alpha values for the interim and final OS analyses are based on Lan-DeMets implementation of the O'Brien-Fleming boundary (Lan and DeMets 1983; O'Brien and Fleming 1979). With one interim analysis at 50% information time point plus one final analysis, the 2-sided alpha-boundaries are 0.00014 and 0.00995, respectively.

If the trial continues after the interim analysis, and if the primary analysis of CR rate is significant at the 0.04 level, the alpha level for the primary analysis of OS will be  $0.04 + 0.00995 = 0.04995 \approx 0.05$ . If the trial continues after the interim analysis, and if the primary analysis of CR rate is not significant at the 0.04 level, the alpha value for the primary analysis of OS will be  $0.00995 \approx 0.01$ . The overall alpha error is controlled at the 0.05 level.

In the unlikely scenario of having observed a significant ( $p \leq 0.00014$ ) positive OS result at the planned interim analysis time point with an acceptable safety profile of guadecitabine, the DMC may choose to analyze the co-primary endpoint CR at an appropriate alpha level to be determined by DMC before making a recommendation to the Company. The Company does not intend to announce the interim analysis results and make any decision to prematurely terminate the study, for any reason other than major safety concerns, without discussing the data and recommendation from the DMC first with the major regulatory agencies.

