## 4.0 SAMPLE SIZE

By trial design, the overall (2-sided) alpha level of 0.05 is split between the co-primary endpoints of CR (0.04) and OS (0.01). A formal interim analysis will be performed only for OS using a group sequential boundary preserving an overall (2-sided) 0.01 alpha level. The sample size calculation for the primary analysis of CR is based on testing at the 0.04 nominal alpha level. If statistical significance is achieved for CR, hierarchically, the final analysis of OS will be conducted to preserve an overall 2-sided 0.05 alpha level, accounting for alpha spent at the interim analysis of OS, as described in Section 11.6.7 and Section 11.9 of the study protocol (see Section 7.3.7 and 7.6). The sample size calculation for OS will be shown for the setting of a 2-sided 0.05 alpha level.

Assuming a CR rate of approximately 0.20 ([Kantarjian et al 2012](#); [Fenaux et al 2010](#); [Burnett et al 2007](#)) for subjects treated in the TC group (all TC therapies combined) and assuming an increase in CR rate to 0.30 or higher can be achieved by treating subjects with guadecitabine,

800 subjects (400 per treatment group) will provide approximately 89% power to detect the overall difference of 0.10 when using a 2-sided Cochran Mantel-Haenszel test having 2-sided alpha level of 0.04. For the purpose of this sample size calculation, the constant CR rates of 0.20 and 0.30 for the TC and guadecitabine groups, respectively, are assumed for each stratum.

For survival, an analysis at 670 death events will provide 90% power to detect a HR of approximately 0.78 (a difference in median survival of 7 months in the TC group versus 9 months in the guadecitabine group), when using a 2-sided stratified log-rank test at an 0.05 alpha level. Accrual is expected to be uniform over a 21 month enrollment period, with an additional follow-up of 12 months. Hence, the assessment of survival needs approximately the same sample size of 800 subjects. Primary response and survival analyses will be performed after 670 death events have occurred. For the purpose of this sample size calculation, a constant HR of approximately 0.78 was assumed for all strata defined by the stratification factors.

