### **5.2 Efficacy Analysis Set**

Efficacy analyses will be based on intent-to-treat (ITT) principle. The Efficacy Analysis Set will include data from all subjects randomly assigned to study treatment. All data will be included and no subjects excluded because of protocol violations. For the analysis of efficacy data, subjects will be included in the treatment group according to their randomly assigned treatment.

For NDAOH, transfusions, and health-related QOL by EQ-5D-5L, the primary analysis will include only the data collected during the first 6 months of the study because, during this study period, subjects are assessed whether or not they are still on study treatment. Secondary analysis may also include data beyond the first 6 months of the study (eg, over the entire period of study treatment).

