## 7.3 Efficacy Variables and Analyses

Efficacy analyses will be based on the Efficacy Analysis Set, except where it is specified otherwise. This section describes the analyses conducted at the primary analysis time point when 670 death events have occurred, assuming that the study continued after the planned interim analysis. The alpha levels referenced in this section are nominal alpha levels for judging statistical significance, taking into consideration the planned interim analysis and the hierarchical testing order of the (final) primary analysis. The overall experimental alpha error is controlled at the 2-sided 0.05 level.

The co-primary efficacy endpoints are CR rate based on IWG 2003 AML Response Criteria ([Cheson et al 2003](#)) and OS. If either of the co-primary efficacy endpoints reaches statistical

significance in favor of guadecitabine at either the interim analysis (OS only) or final analysis (CR and OS), then the study will be considered positive in efficacy.

Secondary efficacy endpoints include CRc, NDAOH, PFS, number of RBC transfusions, and separately, number of platelet transfusions over the duration of the study treatment, the EQ-5D-5L descriptive system and the EQ VAS, as well as duration of CR.

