### 7.3.2 Complete Response

The primary endpoint of CR rate will be calculated as the number of subjects with a best response of CR divided by the total number of subjects included in the efficacy analysis. The CR rate will be compared between the 2 treatment groups using a Cochran Mantel-Haenszel test at an alpha level of 0.04 stratified by the stratification factors used at randomization: age (<75 or ≥75 years), ECOG performance status (0-1, 2-3), study center region (North America, Europe, ROW), and secondary AML (secondary to MDS or other antecedent hematologic disorder) or poor-risk cytogenetics (Yes, No/Unknown). The null and alternative hypotheses are:

- **Null hypothesis  $H_0$ :** CR rates are the same between the guadecitabine treatment and TC treatment
- **Alternative hypothesis  $H_1$ :** CR rates are different between the two treatment arms

A 2-sided  $p$  value of  $\leq 0.04$  will be judged as statistically significant. In addition, a normal approximated, two-sided 96% CI for the (Mantel-Haenszel weighted) difference in CR rates between guadecitabine treatment and TC treatment will be provided (Koch et al 1990).

The following sensitivity analyses will be conducted for the co-primary endpoint of CR rate for evaluating robustness of the treatment effect:

- 1) The CR rate will be compared between the guadecitabine and TC using a regular Chi-square test without stratification.
- 2) A logistic regression analysis will be performed for the primary endpoint of CR with treatment group (guadecitabine or TC), age (<75 or ≥75 years old), ECOG performance status (0-1, 2-3), the geographic region (North America, Europe, ROW) of the study centers, and secondary AML or poor-risk cytogenetics (Yes, No/Unknown) as fixed factors. The point estimate and 95% CI, as well as the  $p$  value will be provided for the odds ratio (OR) comparing the odds of being a responder in guadecitabine treatment with the odds of being a responder in TC treatment.
- 3) An "as-treated" analysis will be conducted on the CR rate, based on treatment actually received as described in Section 5.3, using the same Cochran Mantel-Haenszel test and same

stratification variables described above. Subjects who were randomized but not treated will not be included in this analysis.

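### SAP 7.3.3 gives the OS hazard ratio only a 95% interval although OS may be tested at 0.01; as a lesser point, SAP 7.6 leaves the CR level after an early OS crossing to the DMC

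*SAP*

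**What the plan says.** **OS interval.** SAP 7.3.3 tests OS at 0.05 if CR is significant and at 0.01 if it is not; SAP 7.6 gives the exact final level in the second case as 0.00995. For the Cox hazard ratio, SAP 7.3.3 plans a 95% interval and nothing else. Protocol 11.6.3 plans 95%, or 99% where that is the fitting level. Elsewhere the SAP matches interval to test: 96% for the CR difference, which is tested at 0.04 (SAP 7.3.2), and 95% or 99% for CRc (SAP 7.3.4). SAP 7.0 sets a general default of two-sided 0.05.

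**CR after an early OS crossing.** SAP 4.0 says: "A formal interim analysis will be performed only for OS using a group sequential boundary preserving an overall (2-sided) 0.01 alpha level". SAP 7.3.2 says: "The CR rate will be compared between the 2 treatment groups using a Cochran Mantel-Haenszel test at an alpha level of 0.04". SAP 7.6 then adds a branch that Protocol 11.9 does not have: if OS is significant at the interim (p at or below 0.00014) with acceptable safety, "the DMC may choose to analyze the co-primary endpoint CR at an appropriate alpha level to be determined by DMC". It gives no value, no upper limit and no rule for a later retest. The rule for a trial that goes on is worded without reference to any earlier CR look: "If the trial continues after the interim analysis, and if the primary analysis of CR rate is significant at the 0.04 level", OS receives 0.04 + 0.00995. The test sequence in SAP 7.3.7 also presumes that the study continues. Protocol 4.4 bars the DMC from stopping early on CR, but is silent on testing it.

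**The concern.** The first gap is a departure of the SAP from the protocol on a co-primary endpoint. In the branch where OS must meet 0.00995, a 95% interval can exclude 1 while the formal test is negative. The report would then carry an estimate that looks like a survival benefit next to a result that the plan calls non-significant.

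The second gap is one of prespecification. The level for a co-primary endpoint would be chosen by a committee that has already seen the unblinded OS result. If CR were looked at then and tested again later at the full 0.04, nothing in the text deducts the first look.

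**Working it through.** **Inputs.** From SAP 4.0 and 7.6: 335 and 670 deaths; OS levels 0.00014 and 0.00995; medians 7 and 9 months (hazard ratio 7/9); CR rates 0.20 and 0.30; 400 per arm; CR level 0.04; uniform accrual of 800 over 21 months. Assumed here: exponential survival, and an unstratified approximation to the tests.

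**1. The plan's own figures.**
- Lan-DeMets O'Brien-Fleming spending at half information, 0.005 per side: 2[1 − Φ(2.807/√0.5)] per side, which is 0.000144 two-sided. Solving the bivariate normal for the final look gives 0.00995. Both match SAP 7.6.
- OS power: Φ(√(670/4) × ln(9/7) − 1.960) = Φ(3.253 − 1.960) = 0.902 (stated 90%).
- CR power by a two-proportion test: 0.889 (stated 89%).

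**2. Where interval and test disagree.** The standard error of the log hazard ratio is about 2/√670 = 0.0773. The largest observed hazard ratio that is significant is exp(−z × 0.0773):
- at 0.05, z = 1.960: 0.859
- at 0.00995, z = 2.578: 0.819

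Between these values the 95% interval excludes 1 and the test at 0.00995 is negative. Example: hazard ratio 0.84 has z = 0.1744/0.0773 = 2.26, p = 0.024, 95% interval 0.72 to 0.98, 99% interval 0.69 to 1.02.

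**3. How often.** At a true hazard ratio of 7/9, the chance of landing in that range is 0.9019 − 0.7502 = 0.152. The conflict arises only if CR has also failed. Assuming CR and OS are independent:

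| True CR rate on SGI-110 | P(CR fails) | Joint chance |
|---|---|---|
| 0.30 (planned) | 0.111 | 1.7% |
| 0.25 | 0.641 | 9.7% |
| 0.20 (no effect) | 0.96 | 14.6% |

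**4. Chance of reaching the CR branch.** At 335 deaths and hazard ratio 7/9: Φ(√(335/4) × ln(9/7) − 3.808) = Φ(2.300 − 3.808) = 0.066.

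**5. CR tested at 0.04 at both looks.** Under the planned accrual and medians, 335 deaths fall at month 17.8 with 679 randomised, about 450 of them for at least 6 months. CR information is therefore taken as 450/800 = 0.56 to 679/800 = 0.85 (an assumption). Given a crossing, with CR and OS independent, the CR type I error is 1 − P(|Z1| < 2.054, |Z2| < 2.054) with correlation √t: 0.0655 at 0.56 and 0.055 at 0.85. Averaged over crossing at 7/9:
- 0.04 + 0.066 × (0.0655 − 0.04) = 0.0417
- 0.04 + 0.066 × (0.055 − 0.04) = 0.0410

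With an OS-CR correlation of 0.4 the averages are 0.0435 and 0.0419. Under independence, the average passes 0.05 only if the true hazard ratio is below about 0.68 (information 0.56) or 0.63 (0.85).

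**6. Interim CR levels that hold 0.05.** Suppose the 0.01 from the rejected OS test passes to CR and the final CR test stays at 0.04. Solving 1 − P(|Z1| < z, |Z2| < 2.054) = 0.05 gives an interim level of about 0.019 (information 0.56) to 0.032 (0.85).

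**7. Power of a single CR test at the interim cut.** The analysis set is all randomised subjects, so recent entrants count as non-responders. With 339.5 per arm at 0.04:
- if only the 609 of 679 randomised at least 2 cycles earlier can have responded, rates of 0.20 and 0.30 times 609/679 give 77%
- if only about 450 of 679 can have, power is 61%

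The final analysis has 89%.

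**The case against.** **On the interval.** The OS decision rests on the log-rank p value, not on the interval. A 95% interval is the SAP's declared default, and the SAP also uses it for the sensitivity odds ratio for CR. The SAP says that it is based on protocol version 2, where the 99% option still stands. The first two points stand, and they make this a reporting matter. The third does not remove it: SAP 7.3.3 is the more specific text and would be followed. A reader might also take the 15% from step 3 as the exposure. It is not, because the conflict needs CR to fail as well.

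**On CR.** A reader might infer that SAP 7.6 provides for two unadjusted CR tests and so breaks the 0.05 control. The documents do not say that. SAP 7.6 asks for an appropriate level and states that overall alpha is held at 0.05. It places the look before a DMC recommendation, in a paragraph about possible early termination, and says that the sponsor will consult agencies before any stop on grounds other than major safety concerns. If the trial stops, CR is tested once. Two tests at 0.04 are a scenario that needs a crossing, a DMC choice to test, a trial that continues and no adjustment. What remains is that the stated control has no rule behind it on this branch. The DMC Charter may hold one, but it is not among the documents and SAP 7.6 does not cite it for this.

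A reader might also infer that the CR data set is open, because "Inclusion of additional available data beyond the clinical data cut will be at the discretion of DMC". That sentence describes the OS interim analysis; applying it to CR is conjecture.

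**Conclusion.** Both points hold, and both are minor.

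The OS interval is the firmer one. The SAP drops an option that the protocol gives and that the SAP keeps for CRc. The affected range is an observed hazard ratio of about 0.819 to 0.859 at 670 deaths. The joint chance with CR failure is about 1.7% under planned effects and rises as the CR effect shrinks, assuming independence of CR and OS. No OS decision changes.

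The CR level on the early-crossing branch is unspecified rather than wrong. A single test at 0.05 or less causes no inflation, on the premise that the 0.01 from OS passes to CR. The two-test scenario gives 0.055 to 0.066 given a crossing, but 0.041 to 0.043 averaged at 7/9, for assumed CR information of 0.85 to 0.56 and an OS-CR correlation of 0 to 0.4. Under the global null the added error cannot exceed the 0.00014 chance of crossing. The documents do not support a claim that the familywise level is breached at the planned effect.

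**What to change.** **SAP 7.3.3.** Restore the protocol's choice of a 95% or 99% interval for the OS hazard ratio, with 99% used when OS is tested at 0.01. The cost is a wider interval when CR fails. The same change for the PFS hazard ratio in SAP 7.3.6 would be for consistency only, since the protocol specifies no such interval.

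**SAP 7.6, before the interim.** State the CR level and the retest rule, or cite the DMC Charter if it has them, so that total CR error on this branch stays within 0.05. Options:
- Keep 0.04 at the final analysis and cap the interim CR level at about 0.019 (information 0.56) to 0.032 (0.85). The SAP must then say that the 0.01 from the rejected OS test passes to CR. That 0.01 cannot also fund the 0.01 sequence for CRc, NDAOH and PFS in SAP 7.3.7 if CR fails.
- Test CR once, with no retest. This is simple, but if the one test is at the interim cut, power is about 61% to 77% against 89% at the final analysis.

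Holding both looks within 0.04 is also possible but is not needed for control at 0.05. The cost is SAP wording, Charter wording if it covers this branch, and some DMC flexibility; sample size and conduct do not change.

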## **7.7 Handling of Missing Data and Other Data Anomalies**

No missing data imputations are planned for the study, except as specified. Subjects lost to follow-up will be included in statistical analyses to the point of their last evaluation.

## **7.8 Handling of Protocol Deviations**

Protocol deviations that occur during the study are captured by study monitors and recorded in the CRO's clinical trial management system. Study medical monitors conduct regular reviews of all recorded protocol deviations to ensure the quality conduct of the study. Study medical monitors also identify and categorize important protocol deviations. Important protocol deviations will be summarized by deviation category using counts and percentages. A data listing of all important protocol deviations will also be provided.

